4.2.3. Aim 2: Measures

Baseline and end of treatment. At baseline and end of treatment, the self-reported following will be measured: Demographics (baseline only), smartphone-related information (e.g., operating system), smoking history/status,^{83,93} nicotine dependence using 2-item Heaviness of Smoking Index,^{84,94} smoking-related cognitive and affective processes (e.g., withdrawal symptoms),^{85,95-97} team developed measure of previous experience with contemplative practice developed for [name] study (used in Aim 1),⁸⁶ mindfulness using Avoidance and Inflexibility Scale,⁹⁸ Five Facet Mindfulness Questionnaires,⁹⁹ Self-Compassion Scale,¹⁰¹ affect using Positive and Negative Affect Schedule,¹⁰² depression using Patient Health Questionnaire, anxiety using Generalized Anxiety Disorder-7,¹⁰⁵ and cancer-relevant variables including pain, fatigue, and fear of cancer recurrence.¹⁰⁶⁻¹⁰⁸ Chart abstracted cancer variables (e.g., cancer type) will allow us to describe the heterogeneity in our sample. At the end of treatment, additional items will be assessed: smoking status, nicotine patch

PI: [name] use, changes in smartphone and/or carrier, perceived utility and acceptability of the mindEMI using team-developed items that were used in our team's previous studies (e.g., "How helpful were the mindful skills?")^{86,109-111} as well as validated measures.^{87,112-114} During the end of treatment interview,

open-ended questions on the mindEMI and feedback on the app and format of counseling (e.g., number of treatment sessions) will be assessed using the team developed items (e.g., "What did you like about using the app?").

[figure not shown]
App data. EMA measures will consist of self-reported items on state mindfulness using 3 items selected from extant validated measures,¹¹⁵⁻¹¹⁷ 6 affect items,^{102,118} 1 craving item ("I have an urge to smoke"), using a multiple-point Likert scale, and the number of cigarettes smoked and nicotine patch use (yes/no) as well as psychometrically sound cancer-specific items that include: 1 fatigue item (on a 11-point Likert scale),¹⁰⁷ 1 pain item (on a 11-point Likert scale),¹⁰⁶ and 1 item on fear of cancer recurrence (on a 4-point Likert scale).^{91,108,119,120} The EMAs can be completed in <2 minutes.

4.2.4. Aim 2: Intervention

App used for mindEMI. MetricWire app, by MetricWire (metricwire.com) will be used to deliver the mindEMI. This research-oriented app has been widely used for EMI and EMA studies. Notable strengths of the app include high flexibility in customization of EMA and EMI design and its potential for future scalability (i.e., operates on both Android and iOS).

mindEMI Intervention Content and Logistics. Here we describe the components of the mindEMI.

Formal mindfulness meditations (5-20 minutes) will be in the form of audio recordings in the app; a prompt to complete the meditations will be pushed 1 time/day at a time pre-determined by the participant (i.e., fixed). Meditations will be primarily adopted from feedback from survivors in Study 2a and existing literature.^{74,75} The 'inquiry' exercise to reflect on meditations will be completed 1 time/day, following meditations. Figure 3. Overview of mindEMI and EMA

Brief mindfulness strategies (1-3 minutes) modified in Aim 1 will be delivered in the form of text in 2 ways: (a) when either high cancer-related stress, craving, or NA is indicated via EMA (i.e., prompted at high-risk), and (b) at random. This delivery approach aims to promote the cultivation of mindfulness specifically during high-risk situations, and also more generally when craving/distress may be low. We expect that the meditations will provide a foundation of mindfulness, whereas the strategies will promote the momentary application of mindfulness.

Random EMAs will be pushed 4 times a day. A day will be blocked such that participants can receive up to 6 mindfulness strategies per day, up to 4 of which will be delivered when high risk is detected via EMA (Figure 3). Following prompted strategies at high-risk moments, a follow-up EMA comprised of 4 items (i.e., craving, NA, timing, helpfulness) will be pushed. Both mindfulness strategies and meditations will be available on-demand in the app. The 'inquiry' exercise will also be completed when participants complete on-demand meditations.

4.2.5. Aim 2: Adverse Reactions

Minimal risks are anticipated for this study. Data including self-report and interview (psychological and medical) involve risk of breaches in confidentiality. Participants will always be given the option to refuse to answer any questions on the measures that may be distressing. For Aim 2, data will also be collected via smartphone. As such, there are always risks associated with privacy when collecting data in this format.

Successful abstinence may cause irritability, anxiety, general distress, and difficulty concentrating. The nicotine patch that participants will wear beginning on the guit date in Aim 2 will be the

appropriate dose for their level of smoking, and the patch should aid in the management of withdrawal symptoms. The nicotine patch and smoking cessation counseling have been shown to be safe and effective for smokers attempting to quit (e.g., the patch is available over-the-counter). However, side effects to the patch may occur and include skin irritation/ rash, nausea, dizziness, dry mouth, diarrhea, nervousness, headache, vivid dreams or sleep disturbances, irritability, and irregular heartbeat.

Risks will be protected against as described below. This study involves no investigational drugs or devices.

Emergency procedures will be in place should any psychiatric emergency arise during the screening and/or treatment processes. Although this is likely to be very rare, all study personnel will be trained in these procedures.

Potential side effects from the nicotine patch (Aim 2) will be monitored by study staff and the PI. Participants will be told of potential allergic reactions and side effects in response to the patch and nicotine side effects, and also told that they are free to remove the patch at any point in time. Should participants experience side effects, they will be advised to discontinue the patch, and also told to contact the PI and study staff. Given three phone counseling calls will be scheduled with participants, and that discussion of the patch will be conducted at these times, we do not anticipate any issues with monitoring patch side effects. Additionally, initial eligibility screening will exclude those with medical conditions that are contraindicated for the patch. Research staff will report any potential AEs immediately to the PI. The PI will report AEs to the IRB within five business days using the required reporting format. Any SAEs (using the FDA definition of SAEs) will be reported within two days to the IRB and NIH using the required reporting format. Given the relatively minimal risk nature of the proposed research, this is considered a highly remote possibility. Any IRB actions in relation to this protocol will also be reported to NIH.

					Ye	ar 1 (Mon	th)					Year 2 (Month)												
Activity	1	2	3	4	5	6	7	8	9	10	11	12	1	2	3	4	5	6	7	8	9	10	11	12	
Prepare interview materials, measures, and protocol for Aim 1	х	x	x																						
Aim 1: Recruit participants (N=10) Aim 1: Data collection				x x	x x	8	x x	-	x x	x x															
Develop prototype smartphone app for mindEMI Staff testing the mindEMI										х	x x	x x													
Aim 2: Recruit participants (N=10) Aim 2: Data collection													x x	x x	x x	x x	x x	x x							
Finalize the full version of mindEMI																			х	х	х	х	х	х	

5. STUDY CALENDAR

6. REGULATORY AND REPORTING REQUIREMENTS

6.1. Institutional Review Board

No subject is to be enrolled on this protocol until the Center's Institution Review Board has approved it.

6.2. Monitoring

The Protocol Review & Monitoring Committee will monitor this study.

6.3. Informed Consent

The investigators and the research associated with the study are responsible for obtaining consent by the participants in a manner approved by the Institutional Review Board.

6.4. Investigator Study Files

Research records are the responsibility of the investigator. They will be available for review by the sponsors of the trial, health care personnel involved in this study, the IRB, and the SRC.

6.5. Data Sharing

As required by NIH rules, [name] and her mentoring team will make the data collected in the current project available to outside investigators. Specifically, de-identified data could be used for future research studies or distributed to another investigator for future research studies without additional informed consent. A data-sharing plan has been developed by [name] and her mentoring team to disseminate the research outcomes in a timely manner. Overall, shared data will be made available via mechanisms including NIH-designated Data Repositories (e.g.,

http://www.nlm.nih.gov/NIHbmic/nih_data_sharing_repositories.html) or direct data transfer by Moffitt Research Information Technology (IT) following necessary approvals. The timing of data and resource sharing or public release will follow the corresponding guidelines as outlined in the corresponding NIH policy.

7. STATISTICAL CONSIDERATIONS

7.1. Sample Size/Accrual Rate

Aim 1. Aim 1 will recruit 15-20 cancer survivors who smoke for analyses. We will use an inductive thematic saturation approach, whereby interviews will continue until saturation is met, when no more new information (i.e., the number of new themes) is obtained. The thematic analysis literature recommends the sample size of 6 to 16. Thus, our sample will be 15-20 participants for analyses. Accounting for a drop out rate of ~30%, we will consent 26 participants. [name] will lead the qualitative analysis while consulting with [name] who has expertise in this area; resources available at Moffitt for qualitative analysis will also be used.

Aim 2. Aim 2 will consist of 10 cancer survivors who smoke, independent from Aim 1, to pilot the prototype mindfulness-based ecological momentary intervention (mindEMI). Recommended sample size in usability studies is at least N=10 to capture 94.7% of potential usability problems, which guided the current sample size, accounting for 30% drop out with a desired final sample size of 10 (will recruit N=13).

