3.2. Aim 2: Usability Testing

3.2.1. Participants and Recruitment

Aim 2 will recruit 10 survivors, independent from Aim 1, to pilot the prototype mindEMI. Recommended sample size in usability studies is at least N=10 to capture 94.7% of potential usability problems, which guided the current sample size,⁶⁹ accounting for 30% drop out with a desired final sample size of 10 (will recruit N=13). Recruitment and eligibility will mimic Aim 1, with the addition of a few eligibility criteria. Additional inclusion criteria: (1) Willing to give quitting a try as part of the study; (2) Having a smartphone that allows installation of the app; and (3) Willingness to download and use the app daily. Additional exclusion criteria: (1) current use of smoking cessation medications (e.g., patch, gum, lozenge, nasal spray, inhaler, or any other nicotine replacement products or medications such as Chantix, Zyban, or Wellbutrin with the intent to quit smoking); (2) evidence of current psychosis; and (3) current/planning pregnancy or lactation. During the phone screen, we will ask participants to consult their physicians before nicotine patch use, if they endorse medical conditions (e.g., recent heart attack, heart disease, angina, high blood pressure not controlled by medications, stomach ulcer, diabetes type 1).⁷⁰

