4.2.2. Aim 2: Procedure and Data Collection

Aim 2 will be conducted remotely. Importantly, the mindEMI content will comprise brief mindfulness strategies and meditations selected and/or modified *per survivors' feedback* from Aim 1 and EMA items will assess *both cancer-specific and general smoking relapse vulnerabilities* by including psychometrically sound items including cancer-specific items.⁸⁸⁻⁹¹ Thus, the prototype will be adapted specifically to survivors.

PI: [name]

Study participation will last 4 weeks, with 2 assessments and 3 brief counseling sessions (Figure 2). Participants will be enrolled in the study once they have completed the baseline survey. Treatment will entail brief cessation counseling over the telephone or Zoom conferencing tool per participants' preferences, provision of written cessation materials (i.e., NCI's Clearing The Air booklet),⁹² and nicotine replacement therapy (NRT) in the form of nicotine patch and its instructions (e.g., suggested areas of body to put on) sent via mail; and brief mindfulness strategies/meditations delivered one-week pre-quit and 2 weeks post-quit. The mailout will also include instructions on how to use the app, and details about the study timeline. Meditations will continue 3 weeks post-quit.

Following the phone screen, eligible individuals will provide verbal informed consent and will be scheduled for the 1st counseling session. Baseline measures will be sent via REDCap to be completed online prior to the 1st session, during which participants will be oriented to the app for mindEMI and EMAs. The quit date (QD) will be scheduled for within about one week after the 1st session.

-14 (QD-2W) +21 (QD+3W) +84 (QD+12W) Day -7 (QD-1W) +14 (QD+2W) +/ (QD+1W) (QD) Intervention MBI delivered via Smartphone app Nicotine Replacement Therapy 2nd Brief Counsel 3rd Brief Counsel 1st Brief Counsel Assessment Baseline End of Tx FollowUp Ax [ROO phase only **Ecological Momentary Assessment** Figure 2. Study 2b Participant Flow of mindEMI (Note. QD = Quit Date, W = Week, Ax = Assessment, Tx = Treatment)

The 2nd session will occur around the QD and the 3rd session will take place approximately at the end of treatment (i.e., mindEMI; QD+2W).

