7.2. Data Analysis

Aim 1. Two approaches of qualitative analysis will be used. First, the transcripts will be coded and key themes will be identified by 2 trained study staff. Texts will be analyzed for frequency (number of times the comment was mentioned), extensivity (number of participants making the comment), intensity (expressive strength of the comments), and specificity (degree of clear focus of the comment). A software, NVivo will be used to analyze the data. Coder agreement will be assessed using a Kappa statistic (\geq .80). Second, based on the principles of saturation in qualitative research, details of narratives will also be a focus of analyses. Qualitative analytic strategies such as immersion-crystallization will be implemented, in which the researcher reviews the data both intuitively and reflectively until the most relevant theme to the research questions arises. Descriptive analyses will be conducted on the data collected through survey and chart abstraction (M, SD, %).

Aim 2. The primary outcomes will be participants' open-ended feedback, and perceived utility and likability of the mindEMI based on the Aim 1 benchmarks and retention (\geq 75% through end of treatment). [name] will lead the qualitative thematic content analyses of the feedback and conduct descriptive analyses on usability measures (M, SD, %).

REFERENCES

1. US Department of Health and Human Services: Smoking Cessation: A report of the Surgeon General. Atlanta, GA, U.S. Department of Health and Human Services, Centers for Disease Control and Prevention, National Center for Chronic Disease Prevention and Health Promotion, Office on Smoking and Health, 2020

2. US Department of Health and Human Services: The health consequences of smoking—50 years of progress: a report of the Surgeon General, US Department of Health and Human Services, Centers for Disease Control and Prevention, National Center for Chronic Disease Prevention and Health Promotion, Office on Smoking and Health. Atlanta, GA, 2014

3. National Cancer Institute (NCI): Cancer survivors and smoking, 2018

4. Jassem J: Tobacco smoking after diagnosis of cancer: Clinical aspects. Transl Lung Cancer Res 8:S50, 2019

5. Guimond A-J, Croteau VA, Savard M-H, et al: Predictors of smoking cessation and relapse in cancer patients and effect on psychological variables: An 18-month observational study. Ann Behav Med 51:117-127, 2017

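### Aim 2: recruiting 13 at the plan's own 30% dropout leaves about 9 completers, not the stated final sample of 10

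*Combined protocol and SAP*

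**What the plan says.** The Aim 2 sample size appears in Section 3.2.1 (Participants and Recruitment) and in Section 7.1 (Sample Size/Accrual Rate). Both give the same basis: "Recommended sample size in usability studies is at least N=10 to capture 94.7% of potential usability problems". Both then state the allowance for losses: "accounting for 30% drop out with a desired final sample size of 10 (will recruit N=13").

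Other places give 10 without any allowance:

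- Section 3.2.1 opens with "Aim 2 will recruit 10 survivors, independent from Aim 1, to pilot the prototype mindEMI", so that paragraph uses the verb recruit for both 10 and 13.
- The study calendar table has the row "Aim 2: Recruit participants (N=10").
- The Aim 2 paragraph of Section 1 and the opening sentence of the Aim 2 paragraph in Section 7.1 also give 10 survivors.

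Two further statements bear on who is counted. Section 4.2.2 says "Participants will be enrolled in the study once they have completed the baseline survey". Section 7.2 makes retention a primary outcome with a benchmark of at least "75% through end of treatment", and does not state its denominator.

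**The concern.** A dropout rate is ordinarily a share of the people who start. On that reading, 30% dropout from 13 recruits cannot be expected to leave ten. The figure of 13 is what results from adding 30% to the final sample instead of dividing the final sample by the proportion expected to stay. The document states no formula, so this is an inference from the numbers.

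Ten matters because it is the plan's only quantitative justification for the size of Aim 2, and it is presented as a minimum. If the stated dropout occurs, the pilot is expected to end just below that minimum. The mixed use of 10 and 13 also leaves it unclear whether 10 is a recruitment target or a completer count.

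**Working it through.** **Inputs** (Sections 3.2.1 and 7.1, identical in both): desired final sample 10; dropout 30%; number to recruit 13.

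**Reproducing the plan's figure.** 10 × (1 + 0.30) = 13. This gives the stated number exactly. The Aim 1 figure fits the same pattern: Section 7.1 plans 15 to 20 participants, dropout of about 30% and 26 consented, and 20 × 1.30 = 26.

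**Forward check.** Expected completers = recruits × (1 − dropout):

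- 13 × 0.70 = 9.1
- 14 × 0.70 = 9.8
- 15 × 0.70 = 10.5

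**Backward check.** Recruits needed = final sample / (1 − dropout) = 10 / 0.70 = 14.29, which rounds up to 15.

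**Dropout at which 13 would be enough.** 13 − 10 = 3 losses, and 3/13 = 23.1%.

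**Chance of at least 10 completers.** This is a binomial tail. It assumes that participants drop out independently with a common probability, which the document does not state. The 25% and 20% rows are illustrative; the plan gives only 30% as its dropout assumption.

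| Recruited | Dropout | P(at least 10 complete) |
|---|---|---|
| 13 | 30% | 0.42 |
| 13 | 25% | 0.58 |
| 13 | 20% | 0.75 |
| 14 | 30% | 0.58 |
| 15 | 30% | 0.72 |

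**Link to the retention benchmark.** If the denominator is all 13 recruits, 0.75 × 13 = 9.75, so ten completers are needed (10/13 = 76.9%; 9/13 = 69.2%). On any single shared denominator, the planned 30% dropout means 70% retention, which is below the 75% benchmark. Section 4.2.2 counts enrolment from completion of the baseline survey, so recruits lost before that survey might not enter the denominator. This link is therefore conditional.

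**The case against.** The strongest reply is that the 30% may have been meant as a margin for over-recruitment. On that reading 10 × 1.30 = 13 is exact, and the Aim 1 figure follows the same convention. But the text says "accounting for 30% drop out", and a dropout rate applies to those recruited. The Aim 1 parallel helps explain how 13 arose; it does not make the three figures consistent. Aim 1 is also less exposed, because 26 × 0.70 = 18.2 still lies within its range of 15 to 20. Aim 2 has no range to absorb the shortfall.

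A second reply is that 13 fits the retention the plan hopes for, since 75% of 13 is 9.75, or about ten. That is true, but 75% is a benchmark for success and 30% is the planning assumption. The benchmark does not replace the assumption.

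A third reply is that ten is only a desired number, that the gap is 0.9 of a participant, and that the analysis is descriptive. This stands in full as a statement about weight, and it keeps the point minor. It does not remove the inconsistency, because the plan presents ten as the recommended minimum and contains no rule for replacing dropouts.

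It is also fair to say that the second sentence of Section 3.2.1 largely explains its first, by calling 10 the final sample and 13 the recruited number. The calendar is weak evidence by itself, because its Aim 1 row also gives 10, against 15 to 20 in Section 7.1. Both are matters of tidying.

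**Conclusion.** The concern holds, as a minor point. Thirteen recruits, 30% dropout and ten completers cannot all stand together. On the plan's own dropout rate the expected number of completers is 9.1, a shortfall of 0.9. This arithmetic needs only the ordinary meaning of dropout as a share of those recruited. The probability of 0.42 for reaching ten rests additionally on independent dropout.

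No power or error rate is affected, because Aim 2 is a single-group pilot with no hypothesis test, and the plan ties no decision to the count of ten.

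**What to change.** Use one consistent statement in Sections 3.2.1 and 7.1. There are three ways to reach it:

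- **(a) Keep 13 recruited and 10 completers.** Restate the planned dropout as at most about 23% (3 of 13). The document contains nothing that supports 23%, so a reason for that rate should be added. If retention is counted from all 13 recruits, this option also agrees with the 75% benchmark.
- **(b) Keep 13 recruited and 30% dropout.** Replace the final sample of 10 with about 9 expected completers, and say that this falls just below the stated minimum of ten.
- **(c) Keep 10 completers and 30% dropout.** Replace "will recruit N=13" with 15.

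In the same edit, label 10 as completers and not recruits in the opening sentence of Section 3.2.1 and in the Aim 2 row of the study calendar. Align the Aim 2 paragraph of Section 1 and the opening Aim 2 sentence of Section 7.1 with them. Under (b), change the number itself in all of these places. Stating the denominator for retention in Section 7.2 would settle how the benchmark relates to the recruitment figure.

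Options (a) and (b) cost wording only. Option (c) costs two more participants.

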7.2. Data Analysis

Aim 1. Two approaches of qualitative analysis will be used. First, the transcripts will be coded and key themes will be identified by 2 trained study staff. Texts will be analyzed for frequency (number of times the comment was mentioned), extensivity (number of participants making the comment), intensity (expressive strength of the comments), and specificity (degree of clear focus of the comment). A software, NVivo will be used to analyze the data. Coder agreement will be assessed using a Kappa statistic (\geq .80). Second, based on the principles of saturation in qualitative research, details of narratives will also be a focus of analyses. Qualitative analytic strategies such as immersion-crystallization will be implemented, in which the researcher reviews the data both intuitively and reflectively until the most relevant theme to the research questions arises. Descriptive analyses will be conducted on the data collected through survey and chart abstraction (M, SD, %).

Aim 2. The primary outcomes will be participants' open-ended feedback, and perceived utility and likability of the mindEMI based on the Aim 1 benchmarks and retention (\geq 75% through end of treatment). [name] will lead the qualitative thematic content analyses of the feedback and conduct descriptive analyses on usability measures (M, SD, %).

REFERENCES

1. US Department of Health and Human Services: Smoking Cessation: A report of the Surgeon General. Atlanta, GA, U.S. Department of Health and Human Services, Centers for Disease Control and Prevention, National Center for Chronic Disease Prevention and Health Promotion, Office on Smoking and Health, 2020

2. US Department of Health and Human Services: The health consequences of smoking—50 years of progress: a report of the Surgeon General, US Department of Health and Human Services, Centers for Disease Control and Prevention, National Center for Chronic Disease Prevention and Health Promotion, Office on Smoking and Health. Atlanta, GA, 2014

3. National Cancer Institute (NCI): Cancer survivors and smoking, 2018

4. Jassem J: Tobacco smoking after diagnosis of cancer: Clinical aspects. Transl Lung Cancer Res 8:S50, 2019

5. Guimond A-J, Croteau VA, Savard M-H, et al: Predictors of smoking cessation and relapse in cancer patients and effect on psychological variables: An 18-month observational study. Ann Behav Med 51:117-127, 2017

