Aim 2. To pilot test the mindEMI among cancer survivors. We will obtain feedback from another 10 survivors who will pilot the prototype of mindEMI that will deliver the MBI in real-time at both random moments and when high levels of smoking vulnerability are self-reported via EMA. The primary outcomes will be participants' open-ended feedback along with perceived utility and likability of the mindEMI and retention through the end of treatment.

This novel cessation intervention and demonstration of key feasibility and acceptability benchmarks, combined with the focused training plan, will lead to a future R01 trial of mindEMI for smoking cessation tailored for survivors. Ultimately, the intervention will dismantle cancer-specific and general risk factors of smoking relapse, with high accessibility, scalability, and the ability to intervene in real-time, thus increasing effect.

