4.1.2. Aim 1: Procedure and Data Collection

Survivors (N=15) will complete a single individual in-depth qualitative interview with a brief survey which will last about 1 hour. The thematic analysis literature recommends the sample size of 6 to 16.71,72 Thus, we will recruit 15-20 participants for analyses. The proposed procedures are based on recommendations in the literature and [name] prior qualitative work.^{72,73} Following the phone screen, eligible participants will provide verbal informed consent and will be scheduled for the phone, zoom, or in-person interview per participant's preference. During the interview, the following topics will be addressed: (1) Several key formal mindfulness meditations (e.g., breathing) of various lengths (5-15 minutes) adopted from Mindfulness-Based Cancer Recovery,74 Mindfulness-Based Relapse Prevention,⁷⁵ and [name] studies⁷⁶⁻⁷⁸ will be briefly introduced. Participants will be guided through 1 to 2 meditations, before giving feedback. Participants' perceived utility and acceptability of the meditations will be assessed via a brief scale developed for Time2Quit⁷⁷ (benchmark: ≥75% reporting useful).⁷⁹ (2) Brief mindfulness strategies (content areas: fear of cancer recurrence, pain, fatigue, and self-compassion; each takes 1 to 3 minutes to complete) will be presented. Participants will practice several strategies, after which overall feedback and comprehensibility of the strategy will be obtained. (3) The mHealth component will be introduced. Preferred frequency and timing of the practice and delivery of MBIs, means of delivery (prompted vs user-initiated), and inclusion of MBIs addressing

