4.1.3. Aim 1: Measures

Participants' demographics and perceived utility and acceptability of the meditations and mindfulness strategies will be assessed via a brief scale developed for [name] prior study on a 6-point Likert scale.⁷⁷ (benchmark: ≥75% reporting useful).⁷⁹ Semi-structured interview will ask for the participants' feedback and suggestions on the planned intervention (See the interview guide for specific questions).

In a brief survey, we will use both an established questionnaire as well as questions adapted from previous studies. Participants will complete a survey of demographics (e.g., ethnicity, race, sex, sexual orientation, gender identity, marital status, education, employment status, income), smoking history as assessed by Cancer Patient Tobacco Use Questionnaire (C-TUQ),⁸³ nicotine dependence using Heaviness of Smoking Index,⁸⁴ The Contemplation Ladder,⁸⁵ previous experience with contemplative practice and perceived usability of mindfulness as assessed by the items developed for [name] study,⁸⁶ and perceived usability scale of the Technology Acceptance Model measure.⁸⁷

Additionally, clinical characteristics (e.g., cancer type, date diagnosed with recent cancer) will be assessed by chart abstraction.

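### Are the Aim 2 outcomes of utility and likability left without a benchmark that the analysis can apply?

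*Combined protocol and SAP*

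**What the plan says.** The Specific Aims give the Aim 2 primary outcomes as open-ended feedback together with "perceived utility and likability of the mindEMI and retention through the end of treatment". Section 7.2 repeats the list and ties it to criteria: "perceived utility and likability of the mindEMI based on the Aim 1 benchmarks and retention", with a separate threshold of at least 75% for retention. It plans thematic analysis of the feedback and descriptive statistics (mean, SD, percentage) for the usability measures.

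The benchmark itself is stated in the Aim 1 sections. Section 4.1.3 says that "perceived utility and acceptability of the meditations and mindfulness strategies will be assessed via a brief scale", scored "on a 6-point Likert scale". Both 4.1.2 and 4.1.3 attach a benchmark of at least "75% reporting useful". The scale is cited to reference 77 and the benchmark to reference 79.

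For Aim 2, section 4.2.3 lists "perceived utility and acceptability of the mindEMI using team-developed items", with the example "How helpful were the mindful skills", plus validated measures (references 87 and 112 to 114). The end-of-treatment interview includes the open-ended question "What did you like about using the app".

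**The concern.** Section 7.2 points back to benchmarks, in the plural, and the reader who follows the pointer finds one, worded for usefulness. Three things then seem to be missing.

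- **Likability.** The word appears only in the Specific Aims and in 7.2. The measures sections for both aims speak of utility and acceptability. The one example item about liking is an open interview question, which yields no percentage.
- **Cut-off.** No section says which of the six response points count as useful.
- **Item.** Section 4.2.3 does not name the Aim 1 scale. The helpfulness item and the technology acceptance measure (reference 87) could each be taken to carry the 75%.

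The Specific Aims present feasibility and acceptability benchmarks as part of the lead-in to a later, larger trial. If the item and the cut-off could be picked once the ratings are known, a statement that the benchmark was met would mean little, and two analysts could report opposite verdicts from the same ratings.

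**Working it through.** **Nothing to reproduce.** The 75% is a bare threshold. No sample size, power or error rate in the plan is derived from it.

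**What the threshold means in counts.** The desired final sample is 10 (section 7.1). Smallest passing count = ceil(0.75 × 10) = 8. So 8/10 = 80% passes and 7/10 = 70% fails.

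**Effect of the cut-off.** Assume six ordered points, higher meaning more useful; the labels are not in the protocol. Take ten invented ratings: 3, 3, 4, 4, 4, 5, 5, 5, 6, 6 (mean 45/10 = 4.5).

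| Points counted as useful | Count | Share | Exact 95% CI | Benchmark |
|---|---|---|---|---|
| 4 to 6 | 8/10 | 80% | 44% to 97% | met |
| 5 to 6 | 5/10 | 50% | 19% to 81% | not met |

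The verdict can turn on the cut-off alone. More generally, if m raters score 4 to 6, the stricter rule fails once m − 7 of them score exactly 4: that is 1, 2 or 3 raters for m = 8, 9 or 10.

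**Effect of choosing between two items.** Let the assumed true share be 70%, just below the benchmark. One pre-named item passes with probability P(X ≥ 8 | n = 10, p = 0.70) = 0.383. The better of two items passes with probability between 0.383 (identical answers) and 1 − (1 − 0.383)² = 0.619 (independent answers). At an assumed 60%, the single-item figure is 0.167 and the range is 0.167 to 0.307. The upper ends need independent answers to related questions from the same ten people, which is unlikely.

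**How informative a fully defined benchmark would be.** With item and cut-off fixed, P(X ≥ 8 | n = 10) is 0.383 at a true 70% and 0.678 at a true 80%. With ten raters the pass or fail is a weak signal even when every term is defined. The observed distribution is the more useful result.

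**Reading the sections together.**

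- In 4.1.2 and 4.1.3 the 75% closes a sentence about utility and acceptability, both rated on one brief scale. Section 4.2.3 uses the same pair for Aim 2, and the closing paragraph of the Specific Aims speaks of acceptability benchmarks. Likability in 7.2 is therefore most naturally a loose synonym for acceptability, under that one benchmark.
- The Aim 2 examples are marked as examples. Reference 112, among the validated measures, is by its title a client satisfaction scale, so a rated measure close to liking is already in the battery.
- The timeline puts Aim 1 data collection in Year 1 and Aim 2 in Year 2. Applying the benchmark in Aim 1 requires a decision on which points count as useful, so that decision precedes every Aim 2 rating.
- The denominator is implied to be those with an end-of-treatment rating, because attrition has its own benchmark. As an illustration, if 13 enrol, 10 rate and 8 of them say useful, the all-enrolled share lies between 8/13 = 62% and (8 + 3)/13 = 85%. Reporting retention beside the ratings makes this visible.

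**The case for a change.** The strongest case for a change is that these are primary outcomes, the plan itself chose to hold them to a benchmark, and a few sentences written before Aim 2 starts would close the gap. Reading likability as acceptability still leaves a criterion worded only for usefulness. The scale source cited in Aim 1 (reference 77) is not cited among the Aim 2 measures. The object rated also changes, from practices sampled in an interview to the whole intervention. A percentage needs a dichotomy, and 7.2 gives none.

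Much of this stands as a description of the text. The protocol does not restate the cut-off, does not name the Aim 2 item and uses two words for what seems to be one construct. The freedom to choose an item also remains, as does some freedom over the cut-off if the Aim 2 items use a different response format.

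The step to a required change does not follow. The definition of useful may lie in references 77 or 79 or in the instrument, none of which is available here, so the supportable statement is only that the protocol does not repeat it. Asking the sponsor to write down an item and a cut-off supplies no rule better than the one the team would use anyway. The figures that make the gap look large rest on invented ratings and assumed true shares. With ten raters and the planned means, SDs and percentages, selective emphasis on one item would be at least partly visible.

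**Conclusion.** The concern identifies missing detail and one inconsistent term, not a flaw in the analysis. Run as written, Aim 2 would still give sound descriptive results: themes from the feedback, retention against 75%, and mean, SD and percentage for each usability measure. No test, error rate, sample size or treatment of participants depends on the unstated cut-off, and no go/no-go rule is attached to it.

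The size of the issue is one label. On possible data the words *benchmark met* could rest on 8/10 or be withheld on 5/10, according to the cut-off. That affects how the pilot is described, not what it measured.

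The conclusion assumes that likability stands for acceptability, that the Aim 1 cut-off is carried into Aim 2 where the same scale is reused, and that ratings are reported for all the listed measures and not only the most favourable. The first is the natural reading of the sections together; the other two are ordinary practice. If the team harmonises the term at its next routine revision, that is tidying. No change to the plan is needed.
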